### **Study participants**

Community entry activities to sensitise the chiefs and the general population will be conducted at the beginning of the study through meetings and durbars (Ansah et al., 2015; Ahorlu, et al., 2009). Once the community leaders and the population have accepted the project, the household will be numbered and participants per household will be registered during a household census. All households will be given a unique identification code. Each individual within the household will be assigned a code that links them to a particular household and community. After obtaining consent from the household heads, the children will be enrolled but individual assent and consent will be obtained from the other adolescents and adults in the household. **A cohort of 460 children age 6 months to 15 years will be selected and enrolled into the longitudinal study which will consist of prevalence surveys undertaken before each MTTT. Caregivers of the children in the cohort will be enrolled for the community surveys using questionnaires. In this implementation research the entire population of the seven selected communities will be tested, treated and tracked. This is intended to clear the parasite pool in the community.**

#### **Intermittent preventive treatment for the household members**

The research team **together with Community assistants/volunteers** will conduct **house-to-house** testing (using RDTs) of all children (from 6 months old) and adults residing in 7 selected communities for the presence of malaria parasites. **For this study, the investigators will use the Ag P.f RDT which detects histidinie-rich proteins II antigens (HRP-2 Ag) specific to *P.falciparum* in human blood. The RDTs will be supplied by the Ghana Health service through the National malaria control programme which uses the services of WHO-FIND Lot Testing Programme for quality assurance. Thus, the investigators are using the same RDT that has been procured by the NMCP and are being used routinely in Ghana.** To enable follow up studies in a case where treatment failure is reported, 200ul (two drops) of blood will be collected on filter paper. This will be used to determine immunological parameters such as antibody levels to specific antigens using Polymerase Chain Reaction (PCR) and Enzyme Linked Immunosorbent Assay (ELISA). **RDT confirmed cases who are treated but presents persistent malaria related symptoms such as fever on day 7 will be tested using microscopy and to determine clinical failure. This study is not designed to test for parasite**

**resistance to drug (drug efficacy) and the Project clinicians will advise on the next line of action.** This could be taken up by a masters' student. **However, the student will need to submit a different protocol to the ERC for approval.** All participants confirmed (**using RDTs**) to be carrying the malaria parasite will be treated using ACTs following the Ghana National Malaria Treatment Guidelines and followed up **on days 1, 2, 3 during treatment as DOTs (Directly observed therapy) and on day 7 post treatment.** The research team together with **Community volunteers will be provided the treatment guidelines which specify the dosage for each treatment regimen.** Participants who receive the treatment will be observed for five minutes to ensure that they retain the drug. Those who vomit within this period will have the treatment repeated.

### **Follow-Up**

All treated cases will be followed up **on days 1, 2, 3 during treatment and day 7 post-treatment** to ensure that the participants take the drugs on time as well as document and report all adverse effects.

### **Questionnaire/Focus group Discussion**

The questionnaire will include questions about malaria treatment, prevention and control measures practiced by the household members. Occupants of the household will provide a blood sample for testing. **Focus group discussions will be organized with community members and health care workers to increase the scope of information obtained.**

### **Timely treatment of suspected febrile malaria case in the community**

In order to render operational the home-based management component of the project, two volunteers will be selected from each community and trained on home-based management of malaria and be provided with the protocol, RDTs and ACTs. **The interventions will be carried out quarterly (see the timetable).** Between one MTTT intervention and the next trained community members will provide prompt home-based treatment for children and adults reporting signs and symptoms of malaria and confirmed to be carrying the parasite using RDTs. This will be done using national malaria management protocol. There will be monthly visits by the research team to supervise the community volunteers involved in home-based

management to ensure that the protocol is being respected as well as replenish their stocks. There is a need to visit the health facilities that service the community to enable tracking and linking of medical records with study participants (a master student is required for this component). The investigators hypothesize that a reduction in parasite load in the community will consequently lead to a reduction in the number of hospital malaria related consultations and admissions paving the way for pre-elimination. This will be realised by comparing baseline hospital malaria admission data to evaluation data. **MTTT has already been adopted by the NMCP as one of the control and elimination activities and the investigators are anticipating its being scaled-up in the country, and therefore documenting its implementation challenges will inform the decision in the future.**

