Implementation of rapid scale-up preventive interventions in the past decade has led to a reasonable decrease in the burden of the malaria (WHO 2011) especially given the introduction of the WHO policy of test, treat and track (T3) (WHO 2012). The challenges involved with translating research scenarios into implementation are enormous. It is important to understand the bottlenecks that hinder this process in order to undertake mass testing, treatment and tracking in a large scale using existing health systems, especially in an era when global funding for health services is slowing down (Rao et al. 2013).

Any effective control strategy that interrupts the link between man, the parasite and the vector could seriously reduce the transmission of malaria. In this light, interventions focused on clearing of the parasites in asymptomatic individuals in combination with intensive use of other control measures could pave the way for pre-elimination of the parasite in endemic communities (Bousema et al. 2014). This study aims at reducing the asymptomatic parasitaemia in the Pakro sub district of the Eastern Region of Ghana by conducting MTTT for malaria parasitaemia among household members of age 6 months and older and carrying out targeted treatment of all cases with confirmed asymptomatic parasitaemia or clinical malaria. These interventions intend to follow up enrolled participants over a period of two years. Hospital records will also be studied to document trends in malaria admissions and occurrence of other diseases in the area before and after the interventions.

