### **Specific Objectives**

1. To evaluate the effect of scaling up targeted MTTT/home-based treatment on malaria parasitaemia and hospital consultations and admissions.
2. To determine the prevalence of asymptomatic parasitaemia among afebrile participants.
3. To reduce the burden of malaria in the participating communities.
4. To document challenges which hinder the scale up of mass testing, treatment and tracking of malaria in Ghana.
5. To conduct a cost benefit analysis of the intervention in the area.

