### **Data collection**

Following consent, blood will be drawn from a finger prick. All participants will be tested for the presence of malaria parasites using RDTs. Additionally, blood will be collected on filter paper to enable molecular characterization in case treatment failure is observed in a given patients as explained above. All samples will be stored at NMIMR. To test for anaemia (for children in the cohort study only), a portable automated Hemocue photometer will be used to determine the concentration of Haemoglobin. Anaemia in this study is defined as Hb levels less than 10g/dl. Children with severe anaemia (Hb less than 7g/dl) will be referred to the Pakro Health Centre for follow up. **At evaluation, family members will be asked questions on how much they used to spend on malaria before the intervention and how much they have spent after. Malaria case management records before and after the intervention will be consulted, firstly to determine the change in prevalence and also for cost benefit analysis purposes.**

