### **Data Management and Analysis**

Data Management will be conducted with the support of the Data management unit in the Department of Epidemiology of NMIMR. A database will be created to manage the data. Data will be entered into Epi-info and analysed using SPSS. The unit of enrolment will be the household. Malaria prevalence will be reported as, proportion of subjects identified during the study period with RDT confirmed clinical malaria with

temperature  $\geq 37.5$  or asymptomatic parasitaemia and stratified by subject characteristics, including age, sex and community. A Chi square statistic will be used to compare prevalence across age and gender categories as well as communities.

**To determine whether interventions had an effect on the prevalence of malaria in the area, the baseline prevalence data will be compared with the evaluation data. Also a cost benefit analysis will be conducted by comparing what the NMCP put in in previous years to treat malaria to what it would spend if MTTT is implemented.**

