### ***Expected Outcome/Results***

1. The effect of scaling up targeted MTTT/home-based management on hospital admissions will be understood.
2. The prevalence of asymptomatic malaria parasitaemia among afebrile children aged 6 months to 15 years and adults in the Pakro sub district will be known.
3. Reduced burden of malaria in the participating communities
4. Document challenges that hinder the scale up of mass testing, treatment and tracking of malaria in Ghana.
5. The cost benefit analysis of the scaling up MTTT intervention in the area will be known.

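### Case records cannot determine a change in prevalence, and the before-after facility comparison is not limited to residents of the seven MTTT communities

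*Protocol*

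**What the plan says.** **Use for prevalence.** Protocol, Data collection: "Malaria case management records before and after the intervention will be consulted, firstly to determine the change in prevalence". The same sentence adds the cost-benefit analysis as a second use. Data Management and Analysis describes the quantity itself: "Malaria prevalence will be reported as, proportion of subjects identified during the study period with RDT confirmed clinical malaria with" a temperature of at least 37.5, or asymptomatic parasitaemia.

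**Facility comparison.** Protocol, Timely treatment of suspected febrile malaria case in the community, hypothesises that "a reduction in parasite load in the community will consequently lead to a reduction in the number of hospital malaria related consultations and admissions", and continues: "This will be realised by comparing baseline hospital malaria admission data to evaluation data". Just before this, the section says: "There is a need to visit the health facilities that service the community to enable tracking and linking of medical records with study participants", and notes that a master's student is required for that component. The Introduction says: "Hospital records will also be studied to document trends in malaria admissions and occurrence of other diseases in the area before and after" the interventions. Data mining from the hospital records plans an extraction of malaria admissions from the Health Centre registers: ten years back at baseline, then again after one year and at evaluation.

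**Objective and expected result.** The first specific objective is "To evaluate the effect of scaling up targeted MTTT/home-based treatment on malaria parasitaemia and hospital consultations and admissions". The first expected outcome is narrower: "The effect of scaling up targeted MTTT/home-based management on hospital admissions will be understood".

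**The concern.** Three things do not fit together.

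First, a register of cases is asked to yield a change in prevalence. It moves with care-seeking, access and testing practice as well as with infection.

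Second, the records are described as coming from the area, a term the Protocol does not define. The sub-district has 22 communities and only seven receive MTTT. Counts that include the other 15 would mix treated and untreated populations.

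Third, the intervention changes where people are treated. Volunteers test and treat symptomatic people at home between rounds, so consultations can fall because cases are seen elsewhere.

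The facility part of objective 1 and the first expected outcome are at stake. Mixing in untreated communities would make a real effect look smaller. Cases moving to volunteers would make a fall in consultations look like a larger effect on transmission than occurred. The two act in opposite directions, so neither a fall nor an absence of change could be read as a change in prevalence or parasite load.

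**Working it through.** **1. Can case records give prevalence as described?** The Protocol's description is a proportion of subjects and counts both RDT-confirmed clinical malaria and symptomless parasitaemia. Case records hold people who came for care. They supply no tested population as a denominator and no symptomless carriers. The Project Summary and Rationale themselves hypothesise that symptomless infections outnumber the symptomatic cases in hospital records. On that premise, the records miss the larger part of what is to be measured.

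**2. Share of the sub-district receiving MTTT.**
- Head counts (Sample size): 800 + 1,450 + 1,102 + 323 + 480 + 201 + 129 = 4,485. The Protocol rounds this to 4,500.
- Sub-district population (Study Area): 7,889.
- Share: 4,485 / 7,889 = 0.569. With 4,500 it is 0.570.
- Outside the seven: 7,889 − 4,485 = 3,404, or 43%.
- The numerator is a 2016 head count and the denominator is cited to a 2014 report, so the share is approximate.

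**3. What unrestricted records would show.** Let f be the true relative fall in the seven communities and r their facility use per person relative to the other 15. Assume that sub-district totals are used and that the other 15 do not change:

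shown fall = f × 4,485r / (4,485r + 3,404)

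| f | r = 0.5 | r = 1 | r = 2 |
|---|---|---|---|
| 0.50 | 0.199 | 0.284 | 0.362 |
| 0.80 | 0.318 | 0.455 | 0.580 |

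The 50% fall is illustrative. The 80% fall is the budget's own projection (Treatment) of prevalence from 50% to 10%, (0.50 − 0.10) / 0.50, on the further assumption that facility cases fall in proportion. The values of r are assumptions, because the Protocol gives no attendance figures.

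**4. Home treatment.** The budget (Home-based management of malaria) expects 5 treated cases per community per month: 7 × 5 = 35 a month, and 35 × 24 = 840 over two years. It calls these additional cases, and elsewhere residual and missed ones. Between 0 and 35 consultations a month could therefore be displaced. No facility caseload is given, so this cannot be turned into a percentage.

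**5. Which outcome, and which facilities?**

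| Section | Outcome named |
|---|---|
| Specific Objectives, no. 1 | consultations and admissions |
| Timely treatment, hypothesis | consultations and admissions |
| Timely treatment, comparison | admissions |
| Introduction/Rationale | admissions |
| Expected Outcome/Results, no. 1 | admissions |
| Data mining from the hospital records | admissions |

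The case management records under Data collection might include consultations, but they are assigned to prevalence and cost. The consultation part of objective 1 therefore has no stated comparison. Timely treatment refers to facilities in the plural, Data mining names only the Health Centre, and Study Area lists one Health Centre and two CHPS compounds.

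**The case against.** The strongest reply is that parasite prevalence is measured directly by RDT in the cohort. Study Design assigns the effect on prevalence to those surveys, and the Work Plan's primary and secondary outcomes name no facility-record measure. This stands, and it limits the weight of the point.

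A second reply is that the rule for which register entries count may sit in an analysis plan or data manual that is not shown, and that the linkage sentence points towards study participants. This stands in part. Linkage is expressed as a need, depends on a student and is not tied to the comparison. The instruction under Data collection is different: it is a positive statement, and no later detail would make it right.

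Four stronger readings are tempting and not supported:
- *That the Protocol infers parasite load from hospital data.* The hypothesis runs the other way: lower facility use is a consequence of lower parasite load. Only the Data collection clause draws prevalence from records.
- *That home treatment undermines objective 1.* That objective concerns MTTT and home treatment together, so care moved to volunteers is part of the package effect. The comparison sentence also concerns admissions, on which home treatment bears only indirectly.
- *That the ten-year baseline cannot be linked to participants because study codes begin with the census.* Problems Anticipated describes forms carrying family names and house data tied to house names, so a look-back by name is not excluded. The printed Work Plan dates are also inconsistent: one clearance step precedes proposal development.
- *That the facility result will be diluted to 57% of its true size.* No section says that sub-district totals will be used, and the Health Centre's catchment is not given.

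**Conclusion.** The concern holds in a limited form. The firm part is that case management records cannot determine a change in prevalence as the Protocol describes it; this needs no numerical assumption. It is also firm that the residence scope of the facility comparison is not stated, and that consultations appear in the objective and hypothesis but not in the comparison.

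The size is conditional. With sub-district totals, equal facility use per person and no change in the other 15 communities, a true 50% fall would show as about 28%, or 20% to 36% if relative use is halved or doubled. Displacement to volunteers lies between 0 and 35 consultations a month. It prevents a fall in consultations from being read as a fall in parasite load, and leaves the package effect on facility use intact.

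Because the cohort prevalence result does not rest on these records, this is a minor to moderate point on a supporting outcome, worth correcting before extraction begins.

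**What to change.** - **Data collection:** remove the use of case management records for change in prevalence and rely on the RDT cohort surveys. The cost use can stay.
- **Data mining from the hospital records:** record community of residence and month wherever the registers hold them. Base the before-after comparison on residents of the seven communities. Show other communities descriptively, only if available; they were not randomised and may see spillover.
- **Objective, hypothesis, comparison and expected outcome:** name consultations and admissions as separate outcomes throughout, and state which of the three facilities are covered.
- **Volunteer cases:** show monthly volunteer-treated RDT-positive counts beside the facility counts.
- **Conclusion:** limit what is drawn from these records to the package's effect on facility use.

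The cost is wording changes, two fields in an extraction already budgeted at $2,500, and a count that can be collected at the monthly supervision visits already planned. Abstraction takes modestly longer, more so if the CHPS compounds are added. The Protocol does not say whether the registers record residence; baseline years without it cannot be used. No treatment or sample size changes.

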### **Sample size**

This is an implementation study aimed at enrolling an entire population estimated at 4500 participants from the 7 selected communities in Pakro sub district. This population was obtained following data from a head count in preparation for the mass distribution of LLIN in 2016 - Abase newsite = 800, Fante town = 1450, Adjenase/Kwettey = 1102, Piem/Odumsisi = 323, Adesa/Nsuablaaso = 480, Sacchi/Tabnkro = 201, Odumtokro = 129 (Pakro Health Centre records). However, since the target effect of this intervention is focused at the children age 6 months to 15 years, a community survey with a sample of 368 children will be needed to determine the malaria prevalence projected at 50% in the study population. This has been determined using the formula of Yamane where  $n = N/[1+N(e)^2]$  (Israel 1992) considering a 95% confident level (CI) and  $\pm 5\%$  precision. Assuming a loss to follow up of 10% and a non-response rate of 10%, the sample size is readjusted to 460 children calculated from  $(38/1-0.2)$  for the community survey. At evaluation the available sample size will be determined. This is the group for which questionnaires will be administered. Following a census of the households, children under 6 months to 15 years old will be **randomly selected for the longitudinal cohort study, they will then be** divided into the various age groups 6 months to 11 months, 1-4 years, 5 -10 years and 11-15 years. For each age group the investigators will randomly select 116 children.

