### **Study Design:**

This is an Implementation Research (IR) with a longitudinal cohort design to be undertaken within a two year frame work. The interventions are designed to compare the baseline to evaluation findings following the modified protocol of (Ahorlu et al., 2011). **There are two components to this implementation study a). The longitudinal (cohort) study: This is basically the prevalence surveys to be conducted with the selected cohort of children 6 months to 15 years – at baseline and before each of the subsequent MTTT rounds. b). The Survey involves using structured questionnaire to interview caretakers of children under five to solicit their views on the implementation process perceived benefits and challenges etc.** Though the target group is children from 6 months to 15 years of age, all parasitised adults will be cleared of the parasite during the interventions as well to reduce the parasite reservoirs. **Prevalence of malaria**

**trends in cohort group over the study period will reveal the effect of MTTT scale-up on the children 6month to 15 years.** Between interventions, the teams will conduct homes-based management of malaria for all febrile cases confirmed to be positive for malaria parasites. The challenges faced by the implementation team will be documented at every stage and discussed with all the stakeholders at every stage of the implementation.

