## Treatment

### Survey

The population of the targeted communities is estimated at 4500 people. We estimate 50% prevalence in the first intervention. Assuming a 15% reduction after the first intervention, the second intervention will target 35% prevalence which is expected to drop to 25%. After the third intervention we expect the prevalence to drop to 15% further to 10% after the fourth intervention. The 10% will be used as the prevalence over the next one year. As prevalence decreases the number of cases treated also decrease and consequently the cost. In the course of the different intervention we estimate that we will treat the following number of cases – first intervention  $(0.5 * 4500) = 2,250$ , second intervention  $(0.35 * 4500) = 1,575$ , third intervention  $(0.15 * 4500) = 675$  people. Beginning from the forth intervention we estimate a prevalence of 10% for remaining interventions giving  $(0.1 * 4500) = 450$  cases. Given that after the fourth intervention we have two more interventions, this give us  $(450 * 2) = 900$  cases. The total number of cases to be treated over two years is obtained by adding  $(2250 + 1575 + 675 + 450 + 900)$  cases = 5,850 cases. The course of treating one case is estimated at \$1 giving a total of **\$5,850**.

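### The 460 children and ±5% come from a simple-random-sample formula, but the protocol then words two different draws, one of them equal quotas of 116 per age group to which that precision does not belong

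*Protocol*

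**What the plan says.** The protocol's Sample size section states that "a community survey with a sample of 368 children will be needed to determine the malaria prevalence projected at 50% in the study population". The formula is Yamane's, with a 95% confidence level and ±5% precision. Allowing 10% for loss to follow-up and 10% for non-response raises the number to 460. Study participants repeats that total: "A cohort of 460 children age 6 months to 15 years will be selected and enrolled into the longitudinal study".

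Sample size then describes the draw in consecutive sentences. After the census, children are to be "randomly selected for the longitudinal cohort study, they will then be" split into 6–11 months, 1–4, 5–10 and 11–15 years. Next: "For each age group the investigators will randomly select 116 children".

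The Study Design section makes this cohort the source of the prevalence trend: "This is basically the prevalence surveys to be conducted with the selected cohort of children 6 months to 15 years". Data Management and Analysis defines prevalence as a proportion of subjects and also stratifies it by age, sex and community. Separately, the whole population is covered by "testing (using RDTs) of all children (from 6 months old) and adults residing in 7 selected communities for the presence of malaria parasites".

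**The concern.** The two sentences describe different samples. Selecting first and dividing afterwards gives an approximately self-weighting sample of children, which is what the formula assumes. Drawing 116 in each group gives equal quotas across age groups of very unequal size. A field team cannot do both, and the choice cannot be undone once the children are enrolled.

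The readings produce different cohorts. Under the first, 460 children would include about 15–29 infants; under the second, 116. A pooled proportion then refers to different age mixes, and the protocol's own Introduction says age plays a great role in the malaria burden. The ±5% was calculated for the first reading only. The quota reading also requires a number of infants that seven small communities may not have.

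**Working it through.** **The plan's own figures.** 4500/(1 + 4500 × 0.05²) = 4500/12.25 = 367.3, rounded up to 368. 368/(1 − 0.2) = 460 (the printed working shows 38 for 368, a misprint). Both reproduce. The quotas give 4 × 116 = 464; 460/4 = 115.

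**Inputs not in the protocol.** It gives no counts for the four age groups. The only age share is in the budget explanation (Anaemia): 30% of 4500, or 1350, are under five. Two assumed structures bracket the answer:

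- A: the 1350 spread evenly by year of age, giving 135 aged 6–11 months and 1080 aged 1–4. Ages 5–15 are taken as 20, 25, 30 or 35% of 4500 (900, 1125, 1350, 1575), split 6:5.
- B: all ages proportional to group width (0.5 : 4 : 6 : 5), with 1800–2700 children in total.

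**Infant share.** Quotas: 116/464 = 25%. Structure A: 135/2115 = 6.4% to 135/2790 = 4.8%. Structure B: 0.5/15.5 = 3.2%. A simple random 460 would therefore hold 460 × 0.032 = 15 to 460 × 0.064 = 29 infants.

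**Design effect of equal quotas, census-weighted**, 4 × ΣW², where W is each group's share of the target children: A gives 1.42, 1.33, 1.28, 1.25; B gives 1.29.

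**Half-width** = 1.96 × √[Σ W² p(1−p)/n_h × (1 − n_h/N_h)], with n_h = n/4. The last factor is the finite-population correction (fpc). Here p = 0.50 in every group, and 414 = 460 × 0.9 (non-response only, first survey).

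| n tested | Structure | With fpc | Without fpc |
|---|---|---|---|
| 414 | A | 5.34, 5.18, 5.09, 5.06 | 5.75, 5.56, 5.45, 5.39 |
| 414 | B (1800–2700 children) | 4.96–5.13 | 5.46 |
| 368 | A | 5.71, 5.54, 5.44, 5.41 | 6.10, 5.89, 5.78, 5.71 |
| 368 | B (1800–2700 children) | 5.32–5.48 | 5.79 |

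For comparison, a simple random sample of 368 under A gives 4.64–4.76 with fpc and 5.11 without.

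**If prevalence differs by age.** Setting p = 0.5 everywhere maximises the half-width. Using rates that the Introduction cites from other sites (25% under five; 41.5% or 58.6% at older ages), structure A with 414 tested gives 4.68–4.78 with fpc and 5.01–5.16 without. Crude minus weighted prevalence then runs from +2.5 to −2.2 points, so even its sign is open.

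**Later rounds.** The budget's Treatment section says "We estimate 50% prevalence in the first intervention" and projects 35%, then 15% and 10%. Under A with fpc, 35% with 414 tested gives 4.8–5.1. With 368 tested, 15% gives 3.9–4.1 and 10% gives 3.2–3.4.

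**Can the infant quota be filled?** Under A, 116/135 = 86% of all infants would have to be enrolled, before consent and residence criteria. Under B there are only 0.5/15.5 × 1800 = 58 to 0.5/15.5 × 2700 = 87 infants, fewer than 116.

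**The case against.** The sentence fixing 116 per group is the more specific one and can be read as the operative rule. The gap between 464 and 460 is under 1%. Equal quotas suit the planned comparison across age groups, where each group needs enough children. The effect measure is the change from baseline to evaluation, which this formula does not size, and testing the whole population offers another route to overall prevalence in children.

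On precision, a reader might infer that the cohort misses its ±5% target. The document does not support that. The shortfall requires assumed age shares and the worst-case 50% in every group. Structure B with 1800 children gives 4.96 with fpc, and moderate age differences bring structure A below 5 with fpc. If all 464 were tested, structure A with fpc gives 4.74–4.99. The 30% under-five share is a budgeting estimate, and pairing it with only 20% aged 5–15 is an unusual age structure. None of the figures allows for clustering within households.

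These points stand and keep the effect small. They do not reconcile the two draws or the two totals, and they do not make a simple-random-sample precision apply to equal quotas. At the plan's base number of 368, with 50% in every group, no scenario tested reaches ±5%; the reserve in the 460 is what brings 414 close.

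**Conclusion.** The point holds as a mismatch between the stated size and precision and the stated draw. The contradiction in wording and the totals of 460 and 464 need no outside assumption. Infants at 25% of the cohort against roughly 3–6% of target children, and a design effect of about 1.25–1.4, rest on assumed age structures.

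At 414 tested and 50% in every group the half-width is about 5.0–5.8 points; at 368 it is about 5.3–6.1. Failure to reach ±5% at baseline is possible, not demonstrated. The size and direction of any bias in a crude pooled figure cannot be fixed from the document. Nor is it a finding that the protocol lacks a weighting rule, since an analysis plan may hold one.

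The consequence is small. It falls mainly on overall prevalence at the first survey, and change within the same cohort is less affected. It should still be corrected before children are drawn, because the wording decides who is enrolled and the infant quota may not be attainable.

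**What to change.** - State one draw and one total, for example: from the household census, children aged 6 months to 15 years are listed in four age groups and 115 are drawn at random from each (460). If fewer than 115 eligible infants exist, all are enrolled; state which group receives the unfilled places.
- Delete the wording that selects first and divides afterwards, and the figure of 116.
- Report overall baseline prevalence weighted by census age counts, with a stratified variance, alongside the age-specific results. Equal quotas can stay because they serve the age comparison.
- Replace the ±5% with the precision of that design, calculated from the actual census counts and given with its n and assumed prevalence. The ranges above should not be copied in as fixed values.

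The cost is wording, plus weights from a census already planned. The stated precision may become slightly less favourable. No additional children or tests are required.
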